INVESTIGATIONAL PRODUCT	
A panitumumab-IRDye800 dose of 50 mg, will be systemically infused 1 to 5 days before surgery. Panitumumab-IRDye800 has been manufactured under current good manufacturing practice (cGMP) by LICOR Biosciences Inc. [name] (co-PI) currently holds the IND (119474).
 
On the day before surgery 2 mCi Lymphoseek (^{99m}Tc-tilmanocept) will be administered locally around the primary tumor for sentinel node mapping. Lymphoseek is obtained in unit doses from Cardinal Health.

TREATMENT SCHEDULE	
A panitumumab-IRDye800 dose of 50 mg, will be systemically infused 1 to 5 days before surgery. On the day before surgery, to subjects undergoing sentinel node biopsy, the standard dose of ~2 mCi Lymphoseek will be administered locally around the primary tumor after which lymphoscintigraphy and SPECT/CT imaging will be performed per standard of care to determine the number and location of foci of radiopharmaceutical uptake indicating sentinel nodes.
 
On the day of surgery, intraoperative fluorescence imaging will be performed using an intraoperative optical imaging device (a list of devices is provided in Appendix B). Per standard of care, for the subjects undergoing sentinel node biopsy, a gamma probe will be used to search for radioactive lymph nodes as well. Ex vivo fluorescence imaging and gamma counting of the excised specimens will be performed prior to and after pathological assessment. At all steps, equipment will be used that does not violate or destroy the pathological tissues.

PRIMARY OBJECTIVE(S)	The primary objective of the study is to determine if near-infrared fluorescence imaging of panitumumab-IRDye800 can identify metastatic disease in regional neck lymph nodes of subjects with head and neck squamous cell carcinoma (HNSCC).
SECONDARY OBJECTIVE(S)	Determine if panitumumab-IRDye800 can identify sentinel nodes with the same accuracy as Lymphoseek.

SAMPLE SIZE AND STUDY DURATION	
It is anticipated that 20 subjects will be enrolled into the study. Each subject will be followed for 30 days following the last dose of study medication. Based on the enrollment rate from the panitumumab-IRDye800 trial in HNSCC, it is anticipated that the study will require 2 years to be completed.

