Sentinel node biopsy vs elective regional node dissection: Besides decreased morbidity, SNB offers other advantages over a neck dissection: i) Identification of aberrant draining patterns and “skip metastasis” (35–37); and ii) Improved (micro-) metastasis identification at (histo-)pathology; fewer SNs are harvested which are more meticulously evaluated by the pathologist, resulting in improved diagnostic accuracy (38,39). However, challenges remain: i) Local tracer injection is complicated in areas deep in the oral cavity; ii) Near-injection site SN identification can be challenging due to overshadowing of signal at the primary tumor signal (40,36,22); iii) Often multiple SNs are identified during surgery (22) increasing the risk of complications (41) (eg, nerve damage, lymphedema, scar tissue formation); iv) neck dissection after a positive SNB is complicated due to the presence of scar tissue; and v) A false-negative SNB occurs in 3 to 10% of subjects (ie, the SN is tumor-negative, but at follow-up metastasis in remaining regional LNs are found (42–45). Moreover, although LN mapping is superior to radiographic and clinical exam, it is still limited by the need for direct injection of the dye or radiolabeled compound. **Upstaging with LN assessment can thus only be assessed in tumor types that are accessible for local injection.** This is significant because it influences standard of care (LN surgery or complete lymphadenectomy) in these subject populations only. Identification of regional disease will inform prognostic information and/or determine the need and extent of adjuvant therapies for additional tumor types. Most importantly, however, the tracers used for SNB are not tumor-specific and thus SNB, similar to neck dissection, does not allow for intraoperative tumor-positive LN identification (21,46,47). In fact, **for both SNB and neck dissection (histo-)pathological evaluation is required to determine the presence of (micro-) metastasis and thus a method to intraoperatively identify metastatic LNs is lacking.** Thus, HNSCC subjects would benefit from an alternative technique that, allows for intraoperative lymph node staging.

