2.4.3.3. Intraoperative Imaging Protocol

On the day of surgery, 1 to 5 days post-infusion of panitumumab-IRDye800, intraoperative fluorescence imaging and gamma tracing will be performed.

Optical imaging devices to be used: Imaging with the optical imaging devices will be performed intraoperatively *in situ* and on the back table (see Appendix B for a list of the imaging devices). Additional ex vivo devices will also be used to image the specimens on the back table (see Appendix B for a list of the imaging devices).

All in vivo devices are FDA approved for measuring intraoperative blood flow after indocyanine green (ICG) injection. Because IRDye800 and ICG have overlapping excitation and emission spectra, each device can also be used for imaging subclinical disease based on our preclinical studies in head and neck cancer (see Appendix B for a list of the imaging devices).

Sentinel node biopsy (stage T1/2, cN0)

Step 1) *In situ* gamma tracing and fluorescence imaging of the sentinel nodes:

1. Prior to opening the skin, the surgeon will screen the neck for the presence of radioactive node(s) (ie, SNs) by sweeping the gamma probe over the intact neck. If any radioactive nodes are detected, the location of detected radioactive nodes will be marked on the skin using indelible ink and a still image of the marked will be collected for documentation.
2. After opening the skin, a photo of the neck will be taken for documentation. Hereafter the surgeon will perform fluorescence imaging of the neck to evaluate if there are any fluorescent nodes visible. Fluorescent nodes will be marked on the photo of the neck. Video and still images of the fluorescence imaging procedure will be collected.

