3. Hereafter, as per standard of care, the surgeon will perform SNB using the gamma probe. For this, the surgeon will evaluate the neck with the gamma probe for the presence of radioactive nodes. Upon localizing of radioactive nodes, the count rate of the node will be determined. Then, just prior to the resection of the radioactive node, *in situ* fluorescence imaging will be performed to evaluate the fluorescence-based visibility of the node. For each radioactive node, the respective *in situ* location will be documented (level Ia, Ib, IIa, IIb, III, IV or V) as well as the radioactive status (count rate) and fluorescence status (yes/no). Hereafter the node will be harvested by the surgeon. This process will be repeated until no radioactive nodes are detected anymore *in situ*.

Step 2) Wound bed imaging:

As per standard of care SNB, upon completion of SNB, the neck will be screened once more with the gamma probe as such to determine the presence of any remaining radioactivity (ie, a radioactive signal detected > 10% of the background that correlates with any substrate (node). Areas in the wound bed determined radioactive-positive will be surgically re-evaluated, and, upon checking the fluorescence-status, removed, if deemed necessary by the surgeon. If any nodes are found, gamma tracing will be performed to determine the radioactive status.

Step 3) Pathological imaging:

The fluorescence and/or radioactive status of all excised nodes will be confirmed *ex vivo* on the back table using both a closed-field imaging device and an open-field device as well as the gamma probe, respectively. Hereafter all excised nodal specimens will be sent for (histo-)pathology. After the tissue has been processed and evaluated by the pathologist, imaging findings will be compared to gold-standard histological-assessment performed by the pathologist (including a hematoxylin and eosin (H&E) staining) to determine the correlation between fluorescence, radioactivity and the presence/absence of tumor tissue in the LN(s). Also findings will be compared to preoperative lymphoscintigraphy and SPECT/CT imaging (ie, correlation between preoperative imaging findings and intraoperative imaging findings).

Neck dissection only (T1-4, cN+)

After the neck has been opened by the surgeon, it will be inspected by the surgeon for the presence of suspicious nodes. Real-time fluorescence imaging of the LNs in the neck will then be performed at 4 time points:

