4.7 Criteria for Removal from Study

Treatment will be stopped and subjects will be removed from study due to unacceptable AEs, or withdrawal of consent. Any subject who does not receive the panitumumab-IRDye800 will be considered withdrawn from the study and will not count towards enrollment goals.

Subjects will be considered off study once they have completed the 30-day safety observation period.

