9.2.7 Day 30 (\pm 4 days)

- Investigator or study staff will contact the subject by telephone or review of electronic medical record data to collect any additional adverse events that are attributable to the study and/or concomitant medications.

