12.1.2. Secondary Objective and Endpoint

The **secondary objective** of the study is to determine if panitumumab-IRDye800 can identify LNs with the same efficiency as Lymphoseek.

The **secondary endpoint** is: The number and location of Lymphoseek positive LNs that are also tumor-positive at (histo-)pathology.

To answer the secondary objective: We will determine if the LN tracer Lymphoseek can identify metastatic disease in regional neck LNs of subjects with HNSCC. Similar to the primary analysis, we will calculate the specificity and sensitivity of Lymphoseek for metastatic LN identification, using histology as the gold standard, and compare these to neck dissection with Durkalski's test. Since false negatives are of particular concern, we will calculate the odds of obtaining a false negative using panitumumab-IRDye800 relative to the odds of obtaining a false negative using Lymphoseek-based SNB.

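### Cohort 1 nodes reach histology only if Lymphoseek finds them, so Lymphoseek sensitivity and specificity and the planned false-negative odds ratio are fixed by selection

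*Combined protocol and SAP*

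**What the plan says.** Section 12.1.2 plans Lymphoseek sensitivity and specificity "using histology as the gold standard, and compare these to neck dissection" by Durkalski's test. It then adds that "we will calculate the odds of obtaining a false negative using panitumumab-IRDye800 relative to the odds of obtaining a false negative using Lymphoseek-based SNB". The synopsis carries the same comparison under the name diagnostic odds ratio. Neither place states the unit (node or subject) or a rule for zero cells.

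The nodes that feed these statistics are set elsewhere:

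- Section 3.1 makes the SNB-only and neck-dissection-only criteria mutually exclusive.
- Table 1 (Section 2.4.2) gives Lymphoseek to Cohort 1 only.
- Section 2.4.3.3, SNB Step 1, has the surgeon locate and remove radioactive nodes: "This process will be repeated until no radioactive nodes are detected anymore". Step 2 re-evaluates wound-bed areas only where radioactivity remains.
- For fluorescence seen on opening the neck, the same section says "Fluorescent nodes will be marked on the photo of the neck". No Cohort 1 step removes a fluorescent node that is not radioactive.
- Section 4.7 says "Subjects will be considered off study once they have completed the 30-day safety observation period". The Day 30 contact in Section 9.2.7 is "to collect any additional adverse events that are attributable to the study and/or concomitant medications".

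**The concern.** A false negative of either method can be counted only if a tumor-positive node that the method missed reaches the pathologist. In Cohort 1, Lymphoseek itself decides which nodes reach the pathologist. The table for Lymphoseek against histology then lacks its test-negative row, and accuracy figures computed from it describe the harvest rule, not the tracer.

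The distortion runs one way. A metastatic node that fluoresces but is not radioactive stays in the neck without histology, so it earns fluorescence no credit and costs Lymphoseek nothing. A metastatic node that is radioactive but not fluorescent is counted against fluorescence. Readers could take a reported Lymphoseek sensitivity of about 100% as evidence against panitumumab-IRDye800. The plan itself singles out false negatives as the error that matters most here.

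**Working it through.** **1. The plan's own figures.** Section 12.1.3 assumes 20 subjects, 30 necks, 20 nodes per neck (600 nodes, 30 per subject), intra-class correlation 0.005 and prevalence 7.5%.

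- Effective sample size: 600 / (1 + 29 × 0.005) = 600 / 1.145 = 524.0, as stated.
- Tumor-positive nodes: 524 × 0.075 = 39.3. One-sided exact McNemar power for a 0.2 difference with 0.25 discordance is 0.768 at n = 39 and 0.782 at n = 40, consistent with the stated figure above 78%.

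These figures reproduce, but they credit Cohort 1 with 10 × 1.5 × 20 = 300 nodes, which is a dissection yield and not an SNB yield.

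**2. Lymphoseek against histology under Section 2.4.3.3.**

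| | Tumor-positive | Tumor-negative |
|---|---|---|
| Lymphoseek-positive | TP | FP |
| Lymphoseek-negative | about 0 (not harvested) | about 0 (not harvested) |

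- Sensitivity = TP / (TP + 0) = 100%.
- Specificity = 0 / (0 + FP) = 0%.
- Odds of a Lymphoseek false negative = 0 / TP = 0.

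**3. The planned ratio.** It is x/0 if fluorescence misses a positive node and 0/0 if it misses none. The usual diagnostic odds ratio for Lymphoseek, TP × TN / (FP × FN), is also 0/0. With 3 positive nodes and 1 fluorescence miss, the ratio is (1/2) / (0/3), which is undefined. Adding 0.5 to each cell gives (1.5/2.5) / (0.5/3.5) = 4.2, a value that exists only because of the correction.

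**4. Information in Cohort 1 if it is SNB only.** The documents give no number of sentinel nodes per subject, so I assume 2 to 4. That gives 20 to 40 nodes. At the plan's 5 to 10% prevalence, itself a figure for all harvested nodes, this is 20 × 0.05 = 1 to 40 × 0.10 = 4 tumor-positive nodes. With 4 positives the smallest one-sided exact McNemar p-value is 0.5^4 = 0.0625, so the test cannot reject at 0.05.

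**5. If every Cohort 1 node were examined.** Inputs from Section 2.1 are occult disease in 10 to 30% of cN0 patients, a Lymphoseek false-negative rate of 2.6% with negative predictive value 98%, and a general SNB false-negative figure of 3 to 10%.

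- Rate applied to subjects with occult disease: 10 × 0.10 × 0.026 = 0.03 to 10 × 0.30 × 0.10 = 0.30 expected. The chance of at least one is 1 − 0.9974^10 = 2.6% to 1 − 0.97^10 = 26%.
- From the 98% predictive value: at most 10 × 0.02 = 0.2 expected, and a chance of at most 1 − 0.98^10 = 18%.
- Only if 3 to 10% applies to all subjects: 0.3 to 1.0 expected, with a 26 to 65% chance of at least one.

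**The case against.** The strongest objection is that the documents do not consistently describe Cohort 1 as SNB only. Section 12.1.2 compares Lymphoseek with neck dissection. Section 12.1.3 counts 20 nodes in every neck of all 20 subjects. Section 4.5 places gamma tracing, which is for Cohort 1, before and after a lymphadenectomy. If Cohort 1 did have a dissection, node-level false negatives would be visible. This conflict stands and has to be resolved. It does not rescue the plan as written, because the operative steps and the eligibility rule both describe SNB alone.

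Three stronger readings are tempting but not supported:

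- A reader might infer that the 30-day follow-up is the cause, since Section 2.1 describes a false-negative SNB as one where "the SN is tumor-negative, but at follow-up metastasis in remaining regional LNs are found". That is background on the literature. The same section also describes a Lymphoseek false negative at node level, and the plan's standard is histology. Short follow-up merely closes another route; harvest is decisive.
- A reader might infer that a Lymphoseek false negative is impossible. A node removed incidentally, or found in a re-evaluated wound bed, could prove non-radioactive. Such chance nodes do not make sensitivity estimable.
- A reader might infer that the design hides a likely event, with a 26 to 65% chance. That applies the general SNB rate to all subjects and passes over the Lymphoseek figures in Section 2.1.

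It is also fair that this is a secondary objective in a 20-subject exploratory study, and that the primary fluorescence analysis does not use this ratio.

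**Conclusion.** The concern holds for the secondary analysis. Under Sections 2.4.3.3 and 3.1 as written, Lymphoseek sensitivity of about 100%, specificity of about 0% and a false-negative odds of about 0 are results of selection. Barring an incidental or wound-bed node, the planned ratio is undefined or infinite and cannot favor panitumumab-IRDye800.

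This rests on Cohort 1 being SNB only. Were the documents reconciled toward dissection in Cohort 1, the cells would no longer be empty by design. Ten subjects would still probably give no Lymphoseek false negative, with about 0.03 to 0.3 expected and up to 1.0 only on the least favorable reading of the background rate. A ratio of false-negative odds is therefore a poor summary on either reading.

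**What to change.** 1. Reconcile Sections 4.5, 12.1.2 and 12.1.3 with Sections 2.4.3.3 and 3.1, so that the documents state one procedure for Cohort 1 and the node counts follow from it.
2. If Cohort 1 is SNB only, delete the relative false-negative odds (diagnostic odds ratio) and the Durkalski comparison of Lymphoseek sensitivity and specificity from Section 12.1.2 and the synopsis. State that neither Lymphoseek sensitivity nor specificity is estimable in Cohort 1.
3. Replace them with two proportions: Lymphoseek-positive, tumor-positive nodes (and subjects) that were fluorescent, and Lymphoseek-positive, tumor-negative nodes that were not fluorescent. Give each an exact or cluster-adjusted 95% confidence interval and label it conditional on Lymphoseek localization.
4. Report how many fluorescent, non-radioactive nodes were seen and left without histology.

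The cost is wording in the analysis section and synopsis, plus a count from images already planned. The trial gives up a comparative false-negative claim that its design cannot support.

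Later record review of regional recurrence in Cohort 1 is optional and not part of the required change. It would need a consent and off-study amendment, yield few events, and could run past the planned 24-month completion in Section 3.5. It could not readily be matched by neck level, because Cohort 1 levels are documented only for radioactive nodes.

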12.1.3. Sample Size Justification and Power Considerations

We expect to enroll 10 T1/T2 node-negative subjects and 10 subjects with T1-4 and LN metastasis. Based on the data on LN collection from our current IRB-35064 study, we expect that 50% of subjects will undergo a bilateral neck dissection, meaning we would have a total of 30 necks. Assuming an average of 20 LN harvested per neck we would have a total of 600 LNs. Based on previous findings from our IRB-35064 study, we expect approximately 30-40% of subjects (6 to 8 of 20) will have metastatic LNs with an overall prevalence of 5 to 10% of the total number of harvested LNs (30 to 60 of 600) being tumor-positive.

Since this is a Phase 2 study, power considerations are limited but even so, we have excellent power to detect differences in specificity. Although we will use Durkalski's test to compare sensitivities and specificities, we estimated power by first determining the effective sample size (ESS), adjusting for the correlation of LNs within person, and then estimated power using McNemar's test on this ESS. We assumed an intra-class correlation of 0.005, yielding an effective sample size of 524 LNs. With an effective sample size of 524, a prevalence of 7.5%, a significance level of 0.05, and a 0.25 proportion of discordant pairs, we have greater than 99% power to detect a 0.1 difference in specificities, assuming the lower specificity is 0.8. Similarly, we have greater than 78% power to detect a 0.2 difference in sensitivity with the one-sided McNemar test. This assumes the proportion of discordant pairs is 0.25 and the lower sensitivity is 0.75.

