12. STATISTICAL CONSIDERATIONS

12.1 Statistical Design

12.1.1. Primary Objective and Endpoint

The **primary objective** of the study is to determine if near-infrared fluorescence imaging of panitumumab-IRDye800 can identify metastatic disease in regional neck LNs of subjects with HNSCC.

The **primary endpoint** is: The number and location of panitumumab-IRDye800 positive LNs that are also tumor-positive at (histo-)pathology.

To **answer the primary objective**, we will calculate the sensitivity and specificity of the intraoperative findings on whether the LN is fluorescent (ie, presence of panitumumab-IRDye800) to the histopathological (gold standard) status of the LNs.

We will use the matched pair Durkalski's test (80), accounting for the cluster-correlation within subject, for all sensitivity and specificity comparisons (primary and secondary) using the clust.bin.pair package (81) in the R statistical software (84). Significance for both primary and secondary analyses will be assessed at the 0.05 level and to assess uncertainty, 95% confidence intervals will be provided for all estimates.

Descriptive statistics for continuous characteristics (eg, size of the tumor compartment) will include mean, standard deviation, median, interquartile range, minimum, and maximum values. Frequencies and percentages will be used to summarize categorical data. Graphical tools such as heat maps, histograms, and boxplots will be used to assess distributional properties of continuous variables.

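### The printed sensitivity power of above 78% is one-sided McNemar power on about 40 effective nodes, not power for the planned subject-clustered Durkalski test, whose sidedness is unstated

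*Combined protocol and SAP*

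**What the plan says.** Section 12.1.1 fixes the analysis: "We will use the matched pair Durkalski's test (80), accounting for the cluster-correlation within subject, for all sensitivity and specificity comparisons (primary and secondary"). It adds: "Significance for both primary and secondary analyses will be assessed at the 0.05 level", with 95% confidence intervals. It does not say whether the test is one-sided or two-sided.

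Section 12.1.3 acknowledges that Durkalski's test will be used, but takes power from another test: the nodes are reduced to an effective sample size of 524 (intra-class correlation, ICC, 0.005) "and then estimated power using McNemar's test on this ESS". For sensitivity it concludes: "we have greater than 78% power to detect a 0.2 difference in sensitivity with the one-sided McNemar test". The inputs follow: "This assumes the proportion of discordant pairs is 0.25 and the lower sensitivity is 0.75".

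The same section expects "approximately 30-40% of subjects (6 to 8 of 20) will have metastatic LNs", and 30 to 60 tumor-positive nodes out of 600. Its opening sentence, however, expects 10 subjects with lymph node metastasis. No power is given for Durkalski's test.

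**The concern.** Sensitivity is computed on tumor-positive nodes only, so only node-positive subjects contribute. McNemar's test on an effective sample size treats about 40 such nodes as independent units. Durkalski's test gives each subject one contribution, the net discordance divided by that subject's node count, and takes its variance from those contributions. A subject with one positive node then weighs as much as a subject with 13. With 6 to 8 contributing subjects, the two tests need not have similar power, and a single adjustment of the node total for the ICC reflects neither the small number of subjects nor the spread of nodes among them.

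Section 12.1.2 singles out false negatives as the main worry, so sensitivity is the comparison for which a dependable power statement matters most.

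**Working it through.** **Inputs from section 12.1.3.** 600 nodes in 20 subjects, or 30 per subject; ICC 0.005; prevalence 7.5%; difference 0.2; lower sensitivity 0.75; discordant proportion 0.25; one-sided 0.05 for sensitivity; 6 to 8 node-positive subjects.

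**Discordant cells.** p10 + p01 = 0.25 and p10 − p01 = 0.20, so p10 = 0.225 and p01 = 0.025.

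**Effective sample size.** 600 / (1 + 29 × 0.005) = 600 / 1.145 = 524, as printed. Effective positive nodes: 524 × 0.075 = 39.3. Raw positive nodes: 600 × 0.075 = 45.

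**The plan's figure.** Exact conditional McNemar power, averaged over the binomial number of discordant pairs:

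| Nodes | One-sided 0.05 | Two-sided 0.05 |
|---|---|---|
| 39 | 76.8% | 66.2% |
| 40 | 78.1% | 67.8% |

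The printed figure is the one-sided value at 40 nodes.

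**The planned test.** The plan does not print the statistic; the standard form is X = Σ(b−c)/n ÷ √Σ[(b−c)/n]², summed over subjects, where b and c are a subject's discordant counts and n that subject's positive nodes. Two-sided rejection is |X| > 1.96; one-sided is X > 1.645. Power is by Monte Carlo, with at least 200,000 trials per setting. The even spread is an assumption.

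| Nodes, ICC | Two-sided, 6 / 7 / 8 subjects | One-sided, 6 / 7 / 8 subjects |
|---|---|---|
| 39, ICC 0 | 45 / 54 / 60% | 77 / 80 / 81% |
| 40, ICC 0 | 46 / 55 / 61% | 78 / 81 / 82% |
| 45 (raw), ICC 0.005 | 51 / 60 / 65% | 81 / 84 / 86% |

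At the plan's lower limit of 30 nodes, two-sided power is about 33 to 47%; at its upper limit of 60 it is about 66 to 80% (both across ICC 0 and 0.005). With 10 node-positive subjects it is about 66% (40 nodes) to 72% (45 nodes) two-sided and 84 to 87% one-sided, at ICC 0.005.

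**Uneven counts.** The documents give no distribution of positive nodes across subjects, so these splits are assumptions, with ICC 0.

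| Positive nodes per subject | One-sided | Two-sided |
|---|---|---|
| 3, 4, 5, 6, 7, 7, 8 (mild) | 78% | 51% |
| 1, 2, 3, 4, 6, 10, 13 | 65% | 26% |
| 1, 1, 2, 3, 4, 6, 9, 13 | 65% | 27% |
| 1, 2, 4, 6, 11, 15 | 56% | 12% |
| 1, 2, 4, 5, 7, 11, 15 (45 nodes) | 70% | 32% |

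The four strongly uneven splits span 56 to 70% one-sided and 12 to 32% two-sided. A larger ICC also matters: at an assumed 0.1 with 39 even nodes, one-sided power is 63 to 71%.

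**Type I error.** With p10 = p01 = 0.125 and 39 nodes, two-sided Durkalski rejects in about 3 to 4% of trials with even counts, and in under 1% on the three 39-node uneven splits. With few or unequal clusters the two-sided test is conservative, which helps to explain the low two-sided power.

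**The case against.** The strongest reply is that the only sidedness printed in section 12.1 is one-sided, and that on that setting little is lost. With 40 evenly spread nodes, one-sided Durkalski gives 78 to 82% against 78.1% for exact McNemar, and on the raw 45 nodes the printed figure is conservative. The plan also discloses the McNemar approximation, says that power considerations are limited, and calls the study exploratory.

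Much of this stands. A reader might infer that the planned test has at most 45 to 61% power on the plan's own inputs. The documents do not support that. The range is two-sided, while the plan's sensitivity power is one-sided; and even two-sided, 45 or 60 nodes, or the 10 node-positive subjects also expected, can exceed 61%. Nor is the loss separate from sidedness, since exact McNemar itself falls from 78.1% to 67.8% when made two-sided. Nor is the McNemar figure an upper bound, because one-sided Durkalski exceeds it with 7 or 8 subjects and even counts.

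Three things remain. The one-sided agreement needs fairly even counts, which nothing in the plan supports. It also sets an exact test against a large-sample one: uncorrected large-sample McNemar, which Durkalski's statistic becomes with one node per subject, has about 88% one-sided and 77 to 78% two-sided power on 39 to 40 nodes, so a cost of few subjects shows on both scales. Finally, disclosing an approximation does not make its result a property of the planned test.

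**Conclusion.** The concern holds in limited form. The printed figure is arithmetically correct for the test it names, but that is not the planned test. Whether it carries over depends on a sidedness that section 12.1.1 leaves open and on how positive nodes are distributed across a handful of subjects. It carries over approximately if the test is one-sided and counts are even. It does not if the test is two-sided (45 to 61% on 39 to 40 even nodes, 51 to 65% on the raw 45) or if nodes concentrate in a few subjects.

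These results rest on the standard form of the statistic, the plan's discordance inputs applied to the positive nodes of 6 to 8 subjects, and assumed node distributions. The uneven results show sensitivity to that assumption and do not forecast the trial's power.

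**What to change.** In section 12.1.1, state whether Durkalski's test is one-sided or two-sided. In section 12.1.3, reconcile the 6 to 8 of 20 node-positive subjects with the 10 subjects expected to have lymph node metastasis. Then replace the McNemar figure for sensitivity with simulated power for Durkalski's test at the stated sidedness, using the raw 30, 45 and 60 positive nodes, 6 to 8 and 10 node-positive subjects, and both even and uneven counts labelled as assumptions. Say that the number of node-positive subjects, and the spread of positive nodes across them, limit the sensitivity comparison. If the McNemar figure is kept for reference, it should not be called an upper bound.

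The cost is a short simulation and one rewritten paragraph. The stated power will probably look less favourable. No extra patients are needed.
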